## 6.2 Inclusion Criteria

Each subject must meet all of the following criteria to be enrolled in this study:

- 1. Written and signed informed consent must be obtained before any protocol specific assessment is performed.
- 2. Male or female, aged 18 years or older.
- 3. Has at least 3 of the following symptoms:
  - Cough
  - Production of purulent sputum
  - Dyspnea (shortness of breath)
  - Pleuritic chest pain
- 4. Has at least TWO of the following abnormal vital signs:
  - Fever or hypothermia documented by the investigator (temperature > 38.0°C [100.4°F] or < 36.0°C [95.5°F])
  - Hypotension with SBP < 90 mm Hg
  - Heart rate > 90 beats per minute (bpm)
  - RR > 20 breaths/minute
- 5. Has at least 1 clinical sign or laboratory finding associated with CABP:
  - Hypoxemia ( $PaO_2 < 60 \text{ mm Hg by ABG or oxygen saturation} < 90\%$  by pulse oximetry)
  - Physical examination findings of pulmonary consolidation (eg, dullness on percussion, bronchial breath sounds, or egophony)
  - An elevated total white blood cell (WBC) count (> 12,000 cells/mm^3) or leucopenia (WBC < 4,000 cells/mm^3) or elevated immature neutrophils (> 15% band forms) (regardless of total peripheral WBC count)
- 6. Has disease categorized as being PORT Risk Class III or IV at Screening (see PORT Risk Class calculation in Appendix 5).
- 7. Radiographically-confirmed pneumonia, ie, new or progressive pulmonary infiltrate(s) on chest X-ray (CXR) or chest computed tomography (CT) scan consistent with acute bacterial pneumonia within 48 hours prior to the first dose of test article.

- 8. Is expected to require a minimum of at least 2 days of iv therapy for the initial treatment of CABP.
- 9. Females must have a negative pregnancy test at Screening and agree to comply with using an acceptable method of birth control as per your local requirements (eg, abstinence, po contraceptive, intrauterine device [IUD], barrier contraception [condom], tubal ligation, hysterectomy, bilateral oophorectomy, postmenopausal or vasectomized partner) from Screening through PTE. Males must agree to use an acceptable method of birth control with female partner(s) and must not donate sperm from Screening through PTE.

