## 12.8 Analysis of Additional Efficacy Variables

Additional efficacy analyses will be conducted to support the efficacy findings of the primary and secondary outcomes. CIs will be determined for descriptive purposes, but no conclusions of NI will be made.

The number and percentage of subjects classified as a Clinical Success, Clinical Failure and Indeterminate by the Investigator's Assessment at EOT in the ITT and CE populations (by definition, subjects with an Indeterminate response are excluded from the CE population) will be calculated. A 2-sided unadjusted 95% CI will be constructed for the observed difference in the Clinical Success rate using the method of Miettinen and Nurminen.

The number and percentage of subjects with stabilization of vital signs and clinical signs/laboratory findings associated with CABP at 72-120 hours post first dose of test article will be presented by treatment group in the ITT population. These include body temperature (no fever or hypothermia), SBP (> 90 mm Hg), heart rate (< 90 bpm), RR (< 20 breaths/minute), PaO2 ( $\geq$  60 mm Hg by ABG or oxygen saturation  $\geq$  90% by pulse oximetry), physical exam findings (no findings of pulmonary consolidation), WBC count (< 12,000 cells/mm3 or  $\geq$  4,000 cells/mm3) or immature neutrophils (< 15%).

A summary (number and percentage of subjects) of the assessment of clinical signs and symptoms of CABP at each time point throughout the study will be presented by treatment group in the ITT population. The number and percentage of subjects with resolution of signs and symptoms present at Screening (back to pre-CABP status) will also be provided by study visit. The number and percentage of subjects with no worsening of clinical symptoms of CABP and with the absence of new symptoms of CABP will also be provided by treatment group in the ITT population.

The per-subject and per-pathogen microbiologic outcomes will be provided for the microITT and ME populations at the EOT and PTE visits. Two-sided unadjusted 95% CIs will be provided for the difference in per-subject microbiological favorable outcome rates.

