 - Subjects will be defined as an Indeterminate if the investigator cannot determine whether the subject is a Clinical Success or Failure at the EOT or PTE Visits or the subject has a missing response Table 4. By definition, subjects with an Indeterminate response are included in the denominator for analyses in the ITT and microITT populations, and thus, are considered Clinical Failures. Subjects with an

Indeterminate response are excluded from the CE-EOT, CE-PTE, ME-EOT and ME-PTE populations.

- For microbiologic response:
 - If no post-baseline source specimen is obtained and the subject has an investigator's assessment of Clinical Response, the per-pathogen microbiological response is based on the investigator's assessment of Clinical Response (ie, the response is a presumed response). A per-pathogen microbiological response at the EOT Visit or PTE Visit will be considered Indeterminate only if the Clinical Response at EOT or PTE is also Indeterminate.
- Missing values for other individual data points will remain as missing. Missing values will not be imputed and only observed values will be used in data analyses and presentations.
- Where individual data points are missing, categorical data will be summarized based on reduced denominators (ie, only subjects with available data will be included in the denominators).

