Baseline assessments of clinical symptoms, clinical signs, abnormal vital signs, and abnormal laboratory signs of CABP will be presented for the ITT, Safety, microITT, and CE-PTE populations. The number and percentage of subjects with each of the CABP symptoms (cough, pleuritic chest pain, dyspnea, and phlegm/sputum production) by severity (absent, mild, moderate, severe) will be presented by treatment group. The number and percentage of subjects with the presence by severity (ie, absent, mild, moderate, severe) of the following clinical signs will be provided by treatment group: rales, rhonchi, dullness on percussion, bronchial breath sounds, wheezing, decreased breath sounds, and egophony. The number and percentage of subjects with fever (defined as body temperature > 38°C [100.4°F] oral or rectal), hypothermia (defined as body temperature < 36°C [95.5°F] oral or rectal), hypotension with systolic blood pressure < 90 mmHg, heart rate > 90 bpm, respiratory rate > 20 breaths/min, hypoxemia (defined as PaO₂ < 60 mmHg by arterial blood gas or

oxygen saturation < 90% by pulse oximetry), elevated total WBC count (> 12,000 cells/mm³), leucopenia (WBC < 4,000 cells/mm³), elevated immature neutrophils (> 15% band forms regardless of total peripheral WBC count) and any of elevated total WBC count, leucopenia or elevated immature neutrophils will be summarized by treatment group. Differences between treatment groups will be tested for statistical significance using Fisher's exact test.

Risk factors for CABP will be presented by treatment group for the ITT, Safety, microITT, and CE-PTE populations. Risk factors include smoking (current, past, and descriptive statistics of the number of years since quitting for those subjects who were previous smokers), receipt of pneumococcal vaccine, prior lung infection, whether the subject had mild to moderate COPD, symptomatic asthma with wheezing, and chronic cough with or without sputum production. Differences between treatment groups will be tested for statistical significance using Fisher's exact test for categorical variables and the Wilcoxon rank sum test for continuous variables. Other medical and surgical history will be summarized based on MedDRA system organ class by treatment group for the ITT and Safety populations.

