9.4 Additional Analyses

Additional efficacy analyses will be conducted to support the efficacy findings of the primary and secondary outcomes. CIs will be determined for descriptive purposes, but no conclusions of NI will be made.

Clinical Outcomes

The number and percentage of subjects classified as a Clinical Success, Clinical Failure, and Indeterminate by the Investigator's Assessment at EOT in the ITT and CE-EOT populations (by definition subjects with an Indeterminate response are excluded from the CE-EOT population) will be calculated. The number and percentage of subjects in each response category for the assessment of Clinical response at PTE (based on the investigator's assessment) in the microITT population will also be provided. Two-sided unadjusted 95% CIs will be constructed for the observed difference in the Clinical Success rate using the method of Miettinen and Nurminen (1985).

The number and percentage of subjects with stabilization of all vital signs associated with CABP at 72 to 120 hours post first dose of test article will be presented by treatment group in the ITT population as will the number and percentage of subjects with stabilization of each vital sign. These include temperature (no fever or hypothermia), SBP (> 90 mmHg), heart rate (< 90 bpm), RR (< 20 breaths/minutes), and PaO₂ (> 60 mmHg by pulse oximetry or ABG). WBC count (< 12,000 cells/mm³ or \geq 4,000 cells/mm³) and immature neutrophils (< 15%).

A summary (number and percentage of subjects) of the assessment of clinical symptoms of CABP at each time point throughout the study will be presented by treatment group in the ITT population. Clinical symptoms of CABP (cough, pleuritic chest pain, dyspnea, and phlegm/sputum production) will be summarized as shift tables of score (absent, mild, moderate, and severe) as compared with baseline. Percentages for clinical symptoms will be based on the number of subjects with a baseline and post-baseline evaluation at the time point of the specific clinical symptom. The number and percentage of subjects with resolution of all symptoms present at baseline (back to pre-CABP status) will also be provided by study visit in the ITT population. The number and percentage of subjects with no worsening of clinical symptoms of CABP and with the absence of new symptoms of CABP will also be provided by treatment group and study visit in the ITT population.

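### Every count meets the white-cell rule in the 72–120 h stabilisation analysis; SAP 9.4 also omits the saturation limit, and Clinical Stability (protocol 8.13.2) is in no supplied analysis section

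*SAP*

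**What the plan says.** Protocol 12.8 plans a by-arm ITT table of "stabilization of vital signs and clinical signs/laboratory findings associated with CABP at 72-120 hours". Its oxygen item is PaO2 of at least "60 mm Hg by ABG or oxygen saturation" of at least 90% by oximetry. It continues with "physical exam findings (no findings of pulmonary consolidation), WBC count (< 12,000 cells/mm3 or" at least 4,000, and then immature neutrophils below 15%, joined to the WBC item by *or*.

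SAP 9.4 plans the same table as a composite of all vital signs plus each vital sign singly. After temperature it lists "SBP (> 90 mmHg), heart rate (< 90 bpm), RR (< 20 breaths/minutes"). The oxygen and white-cell text follows: "> 60 mmHg by pulse oximetry or ABG). WBC count (< 12,000 cells/mm³ or" at least 4,000, then immature neutrophils below 15%, this time joined by *and*. The physical-examination item is absent. SAP 9.4 says that confidence intervals in this section are descriptive and that no non-inferiority conclusion will be drawn.

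For baseline, SAP 8.2 counts as abnormal "oxygen saturation < 90% by pulse oximetry), elevated total WBC count (> 12,000 cells/mm³), leucopenia (WBC < 4,000 cells/mm³"), which matches inclusion criterion 5.

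Protocol 8.13.2 defines a separate programmatic outcome, Clinical Stability: temperature up to 37.8°C, heart rate up to 100, respiratory rate up to 24, SBP at least 90, and saturation at least 90% or PaO2 at least 60 on room air. It is to be analysed by day, in the ECR window, at EOT and at PTE. The synopsis lists it among the efficacy assessments.

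**The concern.** A stabilisation rule should separate subjects whose finding has returned within limits from those whose finding has not. The white-cell rule cannot do this, because its two limits are alternatives that together cover the whole scale. The same wording stands in both documents, so neither corrects the other.

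The SAP's oxygen item has a different fault. It states a pressure limit in mm Hg and names oximetry as a source. Elsewhere the documents express oximetry limits as saturation percentages, and SAP 9.4 gives none. The SAP also changes the PaO2 limit from at least 60 to above 60.

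The third matter is an outcome that the protocol defines and promises to analyse, with no planned output in the material supplied.

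At stake is the usefulness of outputs meant to support the primary result at the same time point, and whether whoever programs them must choose a threshold that the plan should have fixed.

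**Working it through.** **White-cell rule.** Inputs: stabilised if x < 12,000 or x ≥ 4,000 (protocol 12.8, SAP 9.4); abnormal at entry if x > 12,000 or x < 4,000 (protocol 6.2 criterion 5, SAP 8.2).

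- To fail the rule as written, a count must satisfy x ≥ 12,000 and x < 4,000 together. No number does.
- Enumeration over the integers 0 to 100,000: 0 of 100,001 counts fail. For example, 500 and 35,000 both pass although both are abnormal at entry.
- With *and* (4,000 ≤ x < 12,000), the 4,000 counts from 0 to 3,999 fail, the 8,000 counts from 4,000 to 11,999 pass, and the 88,001 counts from 12,000 to 100,000 fail. Check: 4,000 + 8,000 + 88,001 = 100,001.
- A count of exactly 12,000 passes the current *or* rule. It would fail the *and* rule although it is not abnormal at entry.

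SAP 7.3 says that, where data points are missing, "categorical data will be summarized based on reduced denominators". The WBC line as written is therefore 100% of subjects with a value, in each arm.

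**Boundary values already unmatched.** Criterion 4 treats "Heart rate > 90 beats per minute (bpm") as abnormal, while SAP 9.4 requires a rate below 90, so 90 is neither abnormal nor stabilised. The same gap exists at three other values:

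| Item | Abnormal at entry | Stabilised | Unassigned value |
|---|---|---|---|
| Heart rate | > 90 | < 90 | 90 |
| Respiratory rate | > 20 | < 20 | 20 |
| SBP | < 90 | > 90 | 90 |
| Bands | > 15% | < 15% | 15% |

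**Oxygen item, side by side.**

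| Source | PaO2 | Oximetry |
|---|---|---|
| Protocol 12.8 | ≥ 60 mm Hg by ABG | saturation ≥ 90% |
| SAP 9.4 | > 60 mmHg | named, no saturation limit |
| SAP 8.2 (abnormal) | < 60 mmHg by ABG | saturation < 90% |

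The Schedule of Events has ABG, or oximetry in its place, at Screening only. Its vital-signs footnote includes oximetry in every vital-signs set. Oximetry is therefore the oxygen measurement scheduled at 72 to 120 hours.

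**Clinical Stability.** Protocol section 12 and SAP sections 5.2, 9 and Appendix 2 contain no such analysis. Two outputs come close:

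- SAP 9.4 uses different limits. Taking fever as above 38.0°C and hypothermia as below 36.0°C (SAP 8.2), heart rates of 90–100, respiratory rates of 20–24, SBP of exactly 90 and temperatures below 36.0°C are within the 8.13.2 limits but not those of 9.4. Temperatures of 37.9–38.0°C are the reverse.
- SAP 8.3 summarises the criteria for the iv-to-oral switch, but not by day or visit.

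Neither document's schedule has vital signs at PTE, although 8.13.2 promises a PTE analysis.

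**The case against.** The best reply is that these are drafting slips in a descriptive tier below the secondary outcomes, and that any programmer would read the white-cell limits as a range. That is fair as to consequence. It does not make the written rule right, and both documents carry it.

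On oxygen, a reader might infer that the SAP admits only ABG values, so that the line would rest on unscheduled blood gases and the composite would be undetermined in subjects who meet everything else. The text does not support this. SAP 9.4 names oximetry as an accepted source, nothing says that oximetry values are discarded, and the missing limit can be found in protocol 12.8 and SAP 8.2. What stands is an omitted cut-off and an altered inequality.

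A reader might also infer that the white-cell rule inflates the composite of all vital signs. The SAP's vital-sign list closes with the oxygen item and a full stop. The white-cell and band text follows as a detached fragment, and neither is a vital sign. The natural reading is a separate row, though the SAP should say so.

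Finally, the absence of Clinical Stability is established only for what was supplied. SAP section 3 refers to a separate EMA SAP and protocol 12.1 to table shells; neither was available.

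**Conclusion.** The point holds, at low severity.

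- **White-cell rule:** wrong as written in both documents. Its size follows from the text and needs no assumption: 100% of subjects with a value, in both arms, if tabulated as written.
- **Oxygen and examination items:** SAP 9.4 departs from protocol 12.8 by omitting the saturation limit, changing the PaO2 inequality and dropping the physical-examination item. The documents support no count of affected subjects.
- **Clinical Stability:** promised in protocol 8.13.2 and absent from the supplied analysis sections, with a PTE commitment that the schedule does not serve. Whether it is planned in a document not supplied cannot be established.

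It would be wrong to read this as a threat to the trial's main conclusion. The primary endpoint is built from four symptoms, survival and antibacterial use, and takes no input from these items. The non-inferiority test, alpha and power are unaffected. Temperature, SBP, heart rate and respiratory rate remain usable singly.

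**What to change.** 1. In protocol 12.8 and SAP 9.4, join the white-cell limits by *and*: at least 4,000 and below 12,000. At the same time settle the value 12,000, which that rule would fail although it is not abnormal at entry, and the existing gaps at bands 15%, SBP 90, heart rate 90 and respiratory rate 20.
2. In SAP 9.4, restore protocol 12.8's oxygen rule: PaO2 at least 60 mm Hg by ABG or saturation at least 90% by oximetry. State whether WBC, bands and physical examination are separate lines or enter the composite, and reconcile the connector between WBC and bands (*or* in the protocol, *and* in the SAP).
3. Add the 8.13.2 outcome by day, in the ECR window and at EOT, or record its omission as a change from the protocol. If it is added, say how the room-air condition is handled and that by-day denominators shrink after discharge. Reconcile the PTE commitment with the schedule.

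The cost is SAP wording, one derived variable, and a correction to protocol 12.8 by amendment or a documented deviation in the SAP. WBC with differential and oximetry are already scheduled at the ECR visit. The documents do not say that room-air status is recorded with each oximetry value, so that should be checked before the 8.13.2 outcome is programmed.

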Per-subject microbiological response at the PTE Visit in the microITT and ME-PTE populations will also be provided for infections caused by monomicrobial and polymicrobial Gram-positive or Gram-negative pathogens, only atypical pathogens, a mixture of both Gram-positive and Gram-negative pathogens, a mixture of Gram-positive and atypical pathogens, or a mixture of Gram-negative and atypical pathogens.

Microbiologic response by baseline pathogen will be determined as the proportion of subjects with a favorable microbiological response (eradication or presumed eradication) at the EOT and PTE Visits for each pathogen isolated at baseline. The number and percentage of subjects in each treatment group with a microbiologically favorable outcome will be tabulated for the microITT, ME-EOT (EOT Visit), and ME-PTE (PTE Visit) populations. Favorable microbiologic response by baseline pathogen will also be summarized separately for pathogens obtained from the blood culture (ie, for bacteremic subjects) for the microITT population.

Microbiological categories for pathogens identified after baseline assessment are superinfection and new infection. The number and percentage of subjects with a superinfection or new infection will be presented by treatment group. A listing will be provided that presents the subjects with a superinfection and new infection including the type of specimen and pathogen.

Decreasing susceptibility of a pathogen is defined as >4-fold increase from baseline to any subsequent study time point in the MIC of the test article received. The number and percentage of subjects in the microITT population with a pathogen showing decreasing susceptibility will be tabulated for each treatment group. In addition, a table will list all subjects in each treatment group with a pathogen showing decreasing susceptibility,

including the type of specimen, pathogen, and MIC values. Additional exploratory microbiological analyses may be conducted.

Health Surveyl Outcomes

At Screening and Final Follow-up visits, the subject will complete a SF-36v2[®] Health Survey (Medical Outcomes Trust, OptumTM). The SF-36v2[®] Health Survey has 8 subscales: physical functioning, bodily pain, role limitations due to physical health problems, role limitations due to personal or emotional problems, emotional well-being, social functioning, energy/fatigue and general health perceptions. It also has a single item that provides an indication of perceived change in health. Physical and mental health composite scores (PCS and MCS) are computed and range from 0 (lowest level of health measured by the scales) to 100 (highest level of health).

The eight SF-36 subscales, PCS, and MCS will be derived in accordance with established norm-based standards for the survey using the software provided by the Medical Outcomes Trust, Optum[™]. Descriptive statistics for the eight subscales, PCS and MCS will be provided at Screening, the Final Follow-up Visit and the change from baseline by treatment group in the ITT Population.

The change from baseline for each of the eight subscale, PCS, and MCS scores will be analyzed using an analysis of covariance model with treatment group as a fixed effect and baseline scaled score as a covariate. Least-squares mean differences, corresponding 95% confidence intervals, and *P*-values were obtained using this model.

9.5 Interim Analysis

No interim analysis of efficacy is planned.

9.6 Subgroup Analyses

The primary analysis (ECR) results will be assessed separately across PORT Risk Class and use of prior antibiotics by treatment group for both the as randomized strata and the actual strata as indicated on the eCRF. For each PORT Risk Class stratum– and prior antibiotic stratum, a 2-sided 95% CI for the observed difference in the Early Clinical Success rates will be calculated for the ITT population.

Results of the assessment of Clinical Response at the PTE Visit (based on the investigator's assessment at the EOT and PTE Visits) will also be assessed across PORT Risk Class and use of prior antibiotics by treatment group for both the as randomized strata and the actual strata as indicated on the eCRF. Separately for each PORT Risk Class stratum and use of prior antibiotics stratum, 2-sided 95% CIs for the observed difference in clinical response in the ITT and CE-PTE populations will be calculated.

10 SAFETY AND TOLERABILITY

All safety analyses will be conducted in the Safety population. Subjects who receive the wrong test article for their entire course of treatment will be analyzed in the group based on the drug received. If a subject receives both omadacycline and moxifloxacin, the subject will be analyzed in the omadacycline arm regardless of the amount of omadacycline received or the randomized treatment assignment. Safety parameters include AEs, vital signs, electrocardiogram (ECG) parameters, and clinical laboratory parameters.

